1.0 Objectives*

1.1 The purpose of our research is to compare the effectiveness of 40mg/ml sodium thiosulfate (STS) solution to normal saline (0.9% sodium chloride) when injected intralesionally for the treatment of calcinosis cutis. Our specific aim is to assess the response of dystrophic and idiopathic calcinosis cutis to the injections of sodium thiosulfate in our patients.

1.2 Our hypothesis is that three injections of STS, each spaced one month apart, will significantly improve our patients' calcinosis cutis condition to a point where they are effectively clear or have a 2-point improvement in their Physician Global Assessment (PGA) scores when compared to normal saline.

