8.0 Study Endpoints*

8.1 Study endpoints:

- Primary:
 - Change in size of study lesions
 - Change in Physician Global Assessment
 - Visual Analog Scale of pain of injection
- Secondary:
 - Adverse Events

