9.2 Timeline

- Subject visits
 - The sodium thiosulfate and saline solution will be prepared the same day as the subject's baseline visit after consent to participate is obtained.
 - Baseline Visit
 - Minute 00-15:
 - Informed consent, HIPAA authorization, and screening and enrollment process.
 - Minute 15-30:
 - Obtain demographics and medical history via Demographics Form and Medical History Form (attached)
 - Selection of 2 lesions of dystrophic or idiopathic calcinosis cutis.
 - Note: The lesions must be at least 2mm in diameter and no larger than 2cm in diameter. If a lesion smaller than 2cm is not available then a 2 cm x 2 cm portion of a larger lesions will be used.
 - One lesion will be "Lesion A", and the other will be "Lesion B" for the entire study duration.
 - Lesions will be labeled with their corresponding letter 'A' and 'B' with a marker and photographed
 - Assessment of calcinosis cutis lesions via Case Report Form (see attached).
 - Administration of STS and normal saline.
 - Minute 30-90:
 - Monitoring of subject for adverse events
- 48-hour follow-up phone call:
 - Minute 0-5:
 - Brief phone call to assess for any adverse reactions

A Comparative Study of the Efficacy of Intralesional Sodium Thiosulfate Versus Intralesional Normal Saline for the Treatment of Dystrophic and Idiopathic Calcinosis Cutis, A Double-Blind Randomized Placebo-Controlled Trial

-
- 1-month (+/- 8 days) Follow-up
 - Minute 00-30:
 - Lesions will be labeled with their corresponding letter 'A' and 'B' with a marker and photographed
 - Assessment of calcinosis cutis via Case Report Form (attached)
 - Administration of STS and normal saline.
 - Minute 30-90:
 - Monitoring of subject for adverse events
 - Debrief of subject
- 2-month (+/- 8 days) Follow-up
 - Minute 00-30:
 - Lesions will be labeled with their corresponding letter 'A' and 'B' with a marker and photographed
 - Assessment of calcinosis cutis via Case Report Form (attached)
 - Administration of STS and normal saline
 - Minute 30-90:
 - Monitoring of subject for adverse events
 - Debrief of subject
- 3-month (+/- 8 days) Follow-up
 - Minute 00-15:
 - Lesions will be labeled with their corresponding letter 'A' and 'B' with a marker and photographed
 - Assessment of calcinosis cutis via Case Report Form (attached)

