 - [name] will not be notified of the result until after completion of the study so as to keep him blinded.
 - The syringes will be labeled with an “A” or “B” label for blinding by [name], or [name].

- Administration of study solutions
 - A volume of 0.1 ml/cm² of normal saline or STS will be injected into each lesion. Therefore, a maximum of 0.4ml of 40mg/ml STS or 16mg of STS (given maximum size of 2 cm x 2 cm) will be used per visit per subject.
 - The same treatment lesion will be injected only with STS every injection and the same control lesion will be injected only with normal saline (0.9% sodium chloride) every injection. In other words, “Lesion A” will always be injected with solution A and “Lesion B” will always be injected with solution B.
 - [name], a board-certified dermatologist, will be administering all injections of STS and normal saline to minimize risks for subjects.

- Disposal Protocol:
 - After use, needles will be disposed of in red sharps container according to UCF Health policy
 - After use, urine samples will be disposed of in the toilet according to UCF Health policy

A Comparative Study of the Efficacy of Intralesional Sodium Thiosulfate Versus Intralesional Normal Saline for the Treatment of Dystrophic and Idiopathic Calcinosis Cutis, A Double-Blind Randomized Placebo-Controlled Trial

9.3 Risk Management:

- Subjects will be directly observed during the administration of the STS and normal saline for any adverse events. An anaphylaxis kit is available in clinic should any subject experience such an event. The principal investigator is certified in basic cardiopulmonary life support and an AED is present in the facility. Subjects will be provided with the phone number of the PI should any issues related to participation in the study arise.
- Sodium thiosulfate is currently FDA-approved for as an antidote in the treatment of cyanide poisoning. FDA phase III studies are currently being conducted for use in calciphylaxis.
- 0.9% Sodium chloride is currently FDA-approved for parenteral replenishment of fluid, diluting or dissolving drugs for intravenous, intramuscular or subcutaneous injection, according to instructions of the manufacturer of the drug to be administered.
- Sterile water is currently FDA-approved as a solvent or diluent vehicle for parenterally administered drugs or solutions and as a source of water for parenteral fluid replenishment after suitable additives are introduced.

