11.0 Data Management* and Confidentiality

11.1 Data will be reported descriptively [mean and standard deviation; median (min-max) and frequency and percentage]. Interrater reliability of PGA will be conducted using Cohen's kappa statistic. As a second step, differences across times and between groups will be explored with non-parametric tests, such as Kruskal-Wallis test and the Mann Whitney U test. Statistical significance will be tested at $p < .05$.

The data will be analyzed for significant differences with aid of a statistician. The results of the data analysis will be graphed for each parameter.

11.2 For our study, we will recruit up to 12 adult male and female volunteers ages 18 years and older. This number is estimated from clinical knowledge of the cases that present to treatment on an annual basis at the research site. Furthermore, a review of the existing literature suggests that the targeted sample size is commensurate to other published studies.^{3,4,13,5-12}

11.3 Data will be managed as follows:

- Data will be stored in the secure HIPAA-compliant database called REDCap.
- Unique identifiers will be created using sequential numbers (i.e. 1, 2, 4 etc.).
- No data collection instrument in REDCap will contain identifying information
- The Screening and Enrollment Log, Drug Accountability Log, Unblinded Treatment Document, Demographics Forms, Medical History Forms, Eligibility Forms Case Report Forms, Independent Observer Case Report Forms, Adverse

A Comparative Study of the Efficacy of Intralesional Sodium Thiosulfate Versus Intralesional Normal Saline for the Treatment of Dystrophic and Idiopathic Calcinosis Cutis, A Double-Blind Randomized Placebo-Controlled Trial

Event Forms (see attached documents) will all be stored in the regulatory binder in a locked drawer in a locked room at UCF Health. Only [name] will have access to this locked drawer.

- Photographs will be taken with a UCF Health digital camera. The photographs will then be transferred to a folder on a password protected HIPAA compliant network drive for clinical research at UCF Health. After transfer of photographs to clinical research folder they will be deleted from the camera. Photographs will be labeled with subject ID number and visits number (i.e Subject 01 3-month)

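### Section 11.1 names only independent-sample tests as examples, although each subject supplies one STS and one saline lesion; a paired test should be named

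*Combined protocol and SAP*

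**What the plan says.** **Design.** Section 9.2 calls for "Selection of 2 lesions of dystrophic or idiopathic calcinosis cutis" in each subject. The allocation is fixed within the subject: "The same treatment lesion will be injected only with STS every injection and the same control lesion will be injected only with normal saline". Sections 7.1 and 9.2 have both lesions assessed at weeks 0, 4, 8 and 12. The treatment groups are therefore matched pairs of lesions, and the time points are repeated measures on the same lesions.

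**Endpoints.** Section 8.1 lists "Change in size of study lesions" and change in PGA among the primary endpoints. Section 1.2 states a responder hypothesis: "effectively clear or have a 2-point improvement in their Physician Global Assessment (PGA) scores when compared to normal saline".

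**Analysis.** Section 11.1 begins with descriptive summaries and Cohen's kappa for agreement on the PGA. The hypothesis tests follow: "differences across times and between groups will be explored with non-parametric tests, such as Kruskal-Wallis test and the Mann Whitney U test", at the .05 level, with a statistician's help. No signed-rank, sign, McNemar or Friedman test is named, and within-subject correlation is not mentioned.

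**Size.** Section 4.1 plans 12 enrolled to give 10 eligible subjects. Section 11.2 bases the number on case volume and published studies, not on a power calculation.

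**The concern.** Within-subject control is the main statistical asset of a trial with about 10 subjects. Section 11.1 names two comparisons, between groups and across times, and the example given for each ignores the pairing or the repetition. An analyst who followed those examples would discard that control.

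Two things are at stake. First, if the two lesions of a subject tend to change together, an unpaired test can miss a real effect that a paired test would detect. Second, the true error rate of an unpaired test then depends on a correlation that nobody has stated. Leaving the choice open also allows the paired or unpaired result to be preferred once the data are seen.

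**Working it through.** The plan has no power figure to reproduce. Its only sample-size step is 12 enrolled for 10 eligible, an allowance for failed screening. The check is therefore a simulation. The number of pairs (10) and the lesion size limits come from the protocol. Effect sizes, correlations, SDs, the number of PGA categories and the loss to 8 pairs are assumptions. Tests are two-sided at 0.05; the protocol does not state sidedness.

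**1. Which correlation matters.** For lesion size and PGA the endpoint is change, so stable subject and lesion effects cancel. With V for variance,

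correlation of changes = V(subject × visit) / [V(subject × visit) + V(residual)].

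With a residual share of 0.20 and a subject-by-visit share of 0, 0.05 or 0.10, this gives 0/0.20 = 0, 0.05/0.25 = 0.20 and 0.10/0.30 = 0.33. Lesions whose values correlate 0.6 at each visit can therefore have changes that correlate only weakly.

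**2. Between treatments: continuous outcome, 1 SD difference, one value per lesion.** Exact critical values: for 10 pairs, U ≤ 23 (size 4.33%) and W ≤ 8 (4.88%); for 8 pairs, U ≤ 13 (4.99%) and W ≤ 3 (3.91%). Bivariate normal outcomes; reruns differ by about a percentage point at most.

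| Correlation of changes | Mann-Whitney type I error, 10 pairs | Power, 10 pairs: Mann-Whitney / signed-rank | Power, 8 pairs: Mann-Whitney / signed-rank |
|---|---|---|---|
| 0 | 4.3% | 51% / 50% | 44% / 35% |
| 0.3 | 1.9% | 52% / 64% | 44% / 47% |
| 0.5 | 0.9% | 53% / 78% | 44% / 61% |
| 0.7 | 0.2% | 55% / 94% | 45% / 82% |

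The two tests break even at a correlation of about 0.04 with 10 pairs and about 0.23 with 8. A sign-flip test with 8 pairs gives 39%, 51%, 66% and 86% down the rows and breaks even at about 0.14. At correlation −0.2, Mann-Whitney's type I error is about 6% with 10 pairs and 7% with 8, above its nominal level.

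**3. Tied score.** Five categories, 1 SD latent difference, correlation 0, 0.3, 0.5 and 0.7, Mann-Whitney / signed-rank:
- 10 pairs: 47% / 36%, 47% / 48%, 47% / 57%, 46% / 73%.
- 8 pairs: 36% / 23%, 33% / 28%, 33% / 36%, 31% / 48%.

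An example by hand: 5 of 10 STS lesions improve equally and no saline lesion does. The paired p is 2 × (1/2)^5 = 0.0625; the tie-exact unpaired p is 0.033.

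**4. Visits pooled as if independent.** Take 10 subjects, a subject variance share of 0.4 and a lesion share of 0.2 to 0.3. Mann-Whitney's type I error is then 5.5% to 8.0% with three visits pooled and 8.2% to 12.4% with four. With a lesion share of 0.1 it stays below 5% (3.2% and 4.5%).

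**5. Across visits.** Section 9.2 sets the size range: "The lesions must be at least 2mm in diameter and no larger than 2cm in diameter". Assume 10 lesions, diameters uniform over 2–20 mm, a linear mean decline of 3 mm by Week 12, and a within-lesion SD of 1, 2 or 4 mm.

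| What is tested | Kruskal-Wallis | Friedman |
|---|---|---|
| Raw diameters, four visits | 0.4%, 0.4%, 1.3% | 99.8%, 66%, 19% |
| Change, four visits, baseline entered as zero | 99.8%, 65%, 18% | 99.9%, 66%, 19% |
| Change, weeks 4, 8 and 12 only | 75%, 15%, 2.4% | 87%, 32%, 11% |

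Subtracting a lesion's own baseline does not alter its within-lesion ranks, so the two four-visit Friedman rows agree apart from simulation error. The model is rough: a 3 mm decline takes lesions under 3 mm, (3 − 2)/18 = 5.6% of them, below zero.

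**The case against.** **The text does not commit to these tests.** They are offered as examples, the comparisons are described as exploratory, and a statistician will be involved. A paired test is compatible with all of that. This stands, and it limits the point to under-specification. It does not remove it, because both examples are of the wrong type for this design and results will be judged at .05.

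**A reader might infer that the named tests always lose power here.** The figures do not support that. With 10 pairs there is nothing to gain near zero correlation. With 8 pairs signed-rank is weaker below about 0.23, and ties can reverse the ranking.

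**A reader might infer that the named tests are at least safe, being conservative.** That needs one value per lesion and a positive correlation. Section 11.1 fixes neither the visit nor the unit of analysis, and the documents say nothing about the correlation.

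**A reader might take the collapse of Kruskal-Wallis from 99.8% to 0.4% as the main result.** It arises only on raw diameters spread over the whole allowed range. Section 8.1 defines the endpoint as change, and Section 11.1 does not say that raw sizes are tested. On change from baseline the loss is nil to moderate. A time trend within one treatment also does not test STS against saline, which is the hypothesis in Section 1.2.

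**Conclusion.** The mismatch is real: the design is paired and repeated, both named examples assume independence, and no paired test is specified. Confidence in that is high. Confidence in the size of the loss is not, because the documents give no correlation, SD or effect size. Under an assumed 1 SD difference with 10 pairs, signed-rank compares with Mann-Whitney as follows: about 1 point lower at correlation 0, then 12, 25 and 39 points higher at 0.3, 0.5 and 0.7. Mann-Whitney is conservative if the two lesions' changes are positively correlated, exceeds its nominal level if they are negatively correlated, and can inflate type I error if visits are pooled. The across-visit loss depends on whether raw size or change is analysed. This should be fixed, at low priority, because the cost is small and the paired analysis fits the design whatever the correlation turns out to be.

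**What to change.** In Section 11.1:

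1. **Lesion size and PGA.** Replace Mann-Whitney U with a Wilcoxon signed-rank or sign-flip test of the within-subject STS-minus-saline difference in change from baseline to Week 12. Enter one value per lesion, state how ties and zeros are handled, and give an estimate with an interval. State that the test relies on symmetry of the differences.
2. **Across visits, if tested.** Replace Kruskal-Wallis with Friedman within each treatment's lesions, as secondary to the comparison of STS with saline.
3. **Responder criterion of Section 1.2, if tested.** Show the paired 2×2 table and use McNemar's exact test. The reason is that it matches the design, not power. It needs at least 6 discordant pairs, all in one direction: 2 × (1/2)^6 = 0.031. With assumed response of 70% against 10%, Fisher's test has 67–68% power and McNemar's 58–63% with 10 pairs; with 8 pairs the figures are about 60% and 32–33%.

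The cost is a short paragraph and no new data. The price in power is small with 10 pairs if the correlation is near zero. It is larger with about 8 pairs (35% for signed-rank against 44% for Mann-Whitney; sign-flip 39%) or with many ties.

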12.0 Provisions to Monitor the Data to Ensure the Safety of Subjects*

12.1 The plan to periodically evaluate the data collected regarding both harms and benefits to determine whether subjects remain safe is as follows:

- The principal investigator and statistician will review cumulative adverse event data after 5 out of 10 subjects have completed the study.
- If there are more severe adverse events in the treatment lesions compared to the control lesions with $p < 0.05$ then the study will be suspended immediately.

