8.2 Primary and secondary safety endpoints

- Primary safety endpoints: Serious adverse event due to IL STS, will be required to withdraw.
- Secondary safety endpoints:

A Comparative Study of the Efficacy of Intralesional Sodium Thiosulfate Versus Intralesional Normal Saline for the Treatment of Dystrophic and Idiopathic Calcinosis Cutis, A Double-Blind Randomized Placebo-Controlled Trial

- Intolerance to pain associated with injections, will be required to withdraw.
- Vasovagal reaction. If a subject develops a vasovagal reaction, he or she will be given the option to withdraw but will not be required to withdraw.
- If a subject experiences a mild to moderate adverse event he or she will be given the option to withdraw but will not be required to withdraw.

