13.0 Withdrawal of Subjects*

A Comparative Study of the Efficacy of Intralesional Sodium Thiosulfate Versus Intralesional Normal Saline for the Treatment of Dystrophic and Idiopathic Calcinosis Cutis, A Double-Blind Randomized Placebo-Controlled Trial

13.1 Subjects will be withdrawn from the research without their consent if they become intolerant to the treatment and/or the researchers determine that they are too nervous, anxious to continue.

13.2 Procedures for orderly termination:

- Subjects may voluntarily terminate their participation in the research at any time by informing a member of the research team.
- A subject may partially withdraw from the study after any of the study visits if the subject is unable or unwilling to do the follow up visits.

13.3 Procedures for subject withdrawal:

- If a subject withdraws or is withdrawn from the study prior to completion, further data collection will be stopped. However, partial data already collected will be used for analysis.
- Orderly termination will proceed at the end of study period for all subjects.

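### The only listed cumulative safety review waits for the fifth completer, so early withdrawals for harm postpone it and, in the extreme, remove it

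*Combined protocol and SAP*

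**What the plan says.** Section 12.1 introduces its monitoring in plural terms: "The plan to periodically evaluate the data collected regarding both harms and benefits to determine whether subjects remain safe is as follows". It then lists a single cumulative review: "The principal investigator and statistician will review cumulative adverse event data after 5 out of 10 subjects have completed the study". The attached rule compares lesions: "If there are more severe adverse events in the treatment lesions compared to the control lesions", at p < 0.05, "then the study will be suspended immediately". The test and its sidedness are not stated. No review is tied to calendar time, to the number of subjects injected or to the occurrence of an event.

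Section 8.2 makes withdrawal compulsory in two situations: "Serious adverse event due to IL STS, will be required to withdraw" and "Intolerance to pain associated with injections, will be required to withdraw". After a vasovagal reaction or a mild to moderate event, the subject may choose to leave. Section 13.1 adds compulsory withdrawal for treatment intolerance or excessive anxiety.

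Section 13.3 says what withdrawal means for follow-up: "If a subject withdraws or is withdrawn from the study prior to completion, further data collection will be stopped". Data already collected are kept for analysis.

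Sections 4.1 and 23.2 plan about 12 enrolments to obtain 10 eligible subjects. The margin is for screen failures, and no section replaces subjects who withdraw after injection.

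**The concern.** The clock for the review counts only subjects who reach the end. Those removed because of a treatment-related serious event or intolerance leave before the end and so do not advance it. Withdrawals can leave the trigger where it is, push it later or remove it, but they can never bring it forward.

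That is the wrong direction for a safety review. Its main use is to protect subjects who still have injections ahead of them. As written, it comes earliest when the injections are well tolerated and later when they are not, by which time few injections may remain to be influenced.

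**Working it through.** The plan gives no calculated figure to reproduce. The trigger of 5 of 10 is stated without derivation, so the check is one of counting and timing.

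**Inputs.** Ten treated subjects (4.1, 23.2). Recruitment takes 10 months (7.1) or less than 8 (20.2), so both are shown. There are three injection visits, at Weeks 0, 4 and 8, and a final visit at Week 12 (7.1), making 30 injection visits in all. Assumptions: even entry, and 4.345 weeks per month.

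**Timing.** Subject k enters at month 0.8k (8-month recruitment) or 1.0k (10-month), for k = 1 to 10. Completion is 12/4.345 = 2.76 months later. If w of the subjects ahead in the queue withdraw, the fifth completer is subject 5 + w, so the review falls at 0.8(5 + w) + 2.76 or 1.0(5 + w) + 2.76. Injection visits scheduled after that date were then counted.

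| Early withdrawals w | Review month (8 / 10) | Enrolled by then (8 / 10) | Injection visits still due (8 / 10) |
|---|---|---|---|
| 0 | 6.8 / 7.8 | 8 / 7 | 9 / 12 |
| 1 | 7.6 / 8.8 | 9 / 8 | 6 / 9 |
| 2 | 8.4 / 9.8 | 10 / 9 | 3 / 6 |
| 3 | 9.2 / 10.8 | 10 / 10 | 1 / 3 |
| 4 | 10.0 / 11.8 | 10 / 10 | 0 / 1 |
| 5 | 10.8 / 12.8 | 10 / 10 | 0 / 0 |

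Example, w = 3 with 8-month recruitment: 0.8 × 8 + 2.76 = 9.16. Only subject 10's Week 8 injection, at 8.0 + 8/4.345 = 9.84, is later. Starting the calendar with the first subject at month 0 and entering one a month gives a similar picture: month 7 with no withdrawals, 8 enrolled and 21 of 30 injection visits done.

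**Which withdrawals matter.** The review moves only if at least one of the first five enrolled withdraws. If w withdrawals fall at random among 10 positions, the share of patterns that cause a delay is 1 − C(5,w)/C(10,w): 50% for one, 78% for two, 92% for three, 98% for four.

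**How likely.** The documents give no withdrawal rate. At an assumed independent risk of 20% per subject:

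- any delay (at least one of the first five withdraws): 1 − 0.8^5 = 67%;
- a shift of three or more places, or cancellation (at least three of the first seven withdraw): 15%;
- no injection visits left, or cancellation: 5.6% with 8-month recruitment (at least four of the first eight) and 2.0% with 10-month (at least five of the first nine).

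**Cancellation.** The review is never due when 10 − w < 5, that is, from w = 6 (10 − 6 = 4). P(at least 6 of 10 withdraw) is 0.6% at a 20% risk, 17% at 40% and 63% at 60%. If all 12 enrolled were treated, eight withdrawals would be needed (12 − 8 = 4).

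**The case against.** Several points on the other side are sound.

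- **Not every harm withdrawal delays the review.** A reader might infer that each one does. Withdrawals only among later subjects leave the trigger unmoved, and a single withdrawal at a random position delays it half the time.
- **Not every subject with a relevant harm must leave.** A reader might also infer that everyone whose event the review looks for is withdrawn. The documents do not support that. The suspension rule concerns *severe* events, whereas compulsory withdrawal concerns *serious* events due to STS, intolerance and anxiety. Section 8.2 has no explicit rule for a severe but non-serious event. Subjects with vasovagal, mild or moderate events may stay, complete and count.
- **Completion is not defined in 12.1.** Section 9.2 uses the word loosely: it schedules the photograph review for when all subjects have completed participation, which can hardly mean that one withdrawal cancels it. Section 13.3 nevertheless contrasts withdrawal with completion, so excluding withdrawn subjects remains the natural reading.
- **Other protection exists.** Subjects are observed at injection and monitored afterwards, asked about events at each visit, and telephoned 48 hours after Visit 1 (9.2, 9.3). Withdrawn subjects' data are kept (13.3), so no events are lost. These checks are made subject by subject, however, and carry no cumulative or between-lesion rule.
- **An earlier review may lack power to suspend.** If severe events occur only in STS lesions, a two-sided exact sign test gives p = 0.0625 with five affected subjects and 0.031 with six. One-sided, five suffice (0.031). This is a limit of an unspecified test, and moving the trigger does not cure it.

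**Conclusion.** The concern holds as a defect of timing. Tied to the fifth completer, the only listed cumulative review can only stay put, slip or disappear as early harm withdrawals accumulate. Under even entry and a 12-week course, each place lost costs 0.8 to 1.0 month. Three early withdrawals cut the injection visits the review could still influence from 9 to 1, or from 12 to 3.

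Two stronger conclusions are not supported. Cancellation is arithmetically possible from six withdrawals among 10 treated subjects without replacement, but it is remote unless tolerability is very poor. Nor does full enrolment mean that no one is left to protect: with three early withdrawals all 10 are enrolled, yet injections remain due.

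The result rests on reading completion as excluding withdrawn subjects, on no replacement, and on assumed even entry. The probabilities also rest on assumed withdrawal risks that have no source in the documents.

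**What to change.** In section 12.1, trigger the review when five injected subjects have either completed the Week 12 visit or been withdrawn for any reason, whichever comes first for each. State that it covers adverse-event data from every subject injected by that date, including those withdrawn and those still in follow-up.

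The review can then fall no later than the fifth injected subject's scheduled completion (month 6.8 or 7.8 above). Withdrawals cannot cancel it once five subjects have been injected.

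The cost is one sentence, with no added visits, staff or subjects. The trade-off is that a review brought forward by withdrawals may rest on fewer completed courses. The withdrawal and suspension rules stay as they are, but *severe* in 12.1 and *serious* in 8.2 must be reconciled, so that it is clear how the events driving suspension relate to those requiring withdrawal.

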- During each visit subjects will be monitored for any adverse events and asked about any potential adverse events since the last visit. Any adverse events will be logged on the Adverse Events Form (see attached).
- Visit 1 will be followed with a 48-hour post-treatment phone call to assess for any adverse events.
- After all subjects have completed their participation, photographs of lesions will be reviewed by [name] who will fill out the Independent Observer Case Report Form (see attached) for each visit. He will be blinded as to which lesions received which treatment and at which visit in the study the lesions were photographed.
- Screening and consent
 - First, each subject will sit down with the principal investigator to discuss the study in depth and review the screening criteria. After all risks, benefits, alternatives, and questions have been discussed consent will be obtained.
 - After the informed consent form is signed, the eligibility screening portion of the case report form will then be filled out by the principal investigator with the research subject. If necessary, a pregnancy test will be performed.

A Comparative Study of the Efficacy of Intralesional Sodium Thiosulfate Versus Intralesional Normal Saline for the Treatment of Dystrophic and Idiopathic Calcinosis Cutis, A Double-Blind Randomized Placebo-Controlled Trial

- Solution preparation
 - 50 ml vials of sodium thiosulfate (250mg/ml) will be used for preparation of the treatment solution.
 - The solution from the bottle will be diluted in a ratio of 1 part sodium thiosulfate 250mg/ml to 5.25 parts sterile water to yield a 40mg/ml solution of sodium thiosulfate.¹⁴ This is done to make the final solution as close to isotonic as possible.
 - 30 ml vials of sodium chloride 0.9% will be used for the control treatment.
 - The solutions will be drawn up in 1 cc syringes utilizing a 25g needle by [name]. The needle will then be replaced with a capped 30g ½ inch needle.
 - All solutions will be drawn up by [name] the day of use and discarded immediately after use.
 - Treatment and control will be randomized once for the entire study and all subjects based upon a one-time flip of a coin as follows:
 - If coin flip is heads: all “A” lesions will receive STS and all “B” lesions will receive normal saline
 - If coin flip is tails: all “A” lesions will receive normal saline and all “B” lesions will receive STS
 - This result will be recorded on the Unblinded Treatment Document (See attached).

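### The only prespecified study-level suspension rule, p < 0.05 at one look after five completers, names no test or sidedness and can almost never act under an exact paired test

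*Combined protocol and SAP*

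**What the plan says.** Section 12.1 introduces "The plan to periodically evaluate the data collected regarding both harms and benefits" but schedules one review: "The principal investigator and statistician will review cumulative adverse event data after 5 out of 10 subjects have completed the study". The only stated trigger is that the study is suspended "If there are more severe adverse events in the treatment lesions compared to the control lesions" with p < 0.05. The section gives no test, does not say whether p is one- or two-sided, and does not say whether lesions with an event or individual events are counted.

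The nearest statement on tests is in Section 11.1: "differences across times and between groups will be explored with non-parametric tests, such as Kruskal-Wallis test and the Mann Whitney U test". These are examples for exploring the data, they are unpaired, and the section does not link them to the safety rule.

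Other provisions act on the individual subject:
- Section 8.2: "Serious adverse event due to IL STS, will be required to withdraw".
- Section 9.2: "During each visit subjects will be monitored for any adverse events and asked about any potential adverse events since the last visit". It also provides an hour of observation after each treatment and a 48-hour call after Visit 1.
- Section 13.3: "If a subject withdraws or is withdrawn from the study prior to completion, further data collection will be stopped". Data collected up to that point are kept.

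**The concern.** This is the only rule written in advance that would stop further subjects from being injected. Whether it acts on given data depends on a choice of test that the plan leaves open, so that choice could be made after the data are seen. Under an exact test that respects the pairing, the rule has almost no chance of acting with five subjects.

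Three features weaken it further.
- It waits for completers, so a subject withdrawn for a serious STS-related event does not bring the look closer.
- Section 13.3 then ends data collection on that subject, just when follow-up matters most.
- The systemic risks listed in Section 14.1, such as hypotension and disorientation, cannot be assigned to a lesion when both solutions go into the same person. They are reviewed but cannot enter the comparison.

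**Working it through.** The plan gives no operating characteristics for the rule, so there is no figure to reproduce.

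**Inputs.** Five completers, one lesion per treatment each, so 5 pairs (Sections 9.2, 12.1). Threshold p < 0.05 (Section 12.1). Treatment is "three injections of STS, each spaced one month apart" (Section 1.2), with three months of participation (Section 7.1). Recruitment takes ten months (Section 7.1) or under eight (Section 20.2). The documents give no severe-event rate for lesions. I assume 10%, 30% or 50% of subjects have a severe event on the STS lesion and none on the saline lesion.

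**1. Exact paired test.** For a k-0 split, one-sided p = 0.5^k and two-sided p = 2 × 0.5^k.
- 4-0: 0.0625 and 0.125.
- 5-0: 0.031 and 0.0625.

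The two-sided test cannot trigger with 5 pairs. The one-sided test needs 5-0.

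**2. Fisher, 5 v 5 (ignores pairing).** One-sided p = C(5,k)/C(10,k); two-sided is double.
- 3-0: 10/120 = 0.083 and 0.167.
- 4-0: 5/210 = 0.024 and 0.048.

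Fisher needs 4-0 with either sidedness.

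**3. The 3-0 split under other choices.**

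| Test | Two-sided p | One-sided p |
|---|---|---|
| Exact paired | 0.25 | 0.125 |
| Fisher | 0.167 | 0.083 |
| McNemar approximation, uncorrected | 0.083 | 0.042 |
| Mann-Whitney, continuity corrected | 0.067 | 0.033 |
| Boschloo | 0.062 | 0.031 |
| Barnard | 0.058 | 0.029 |
| Mann-Whitney, uncorrected | 0.0495 | 0.025 |

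For Mann-Whitney, the one test named in Section 11.1 that compares two groups, the two-sided answer turns on the continuity correction.

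**4. Chance of triggering at 5 subjects.** Binomial upper tails, n = 5.

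| Split needed | Which tests | 10% | 30% | 50% |
|---|---|---|---|---|
| none suffices | two-sided exact paired | 0% | 0% | 0% |
| 5-0 | one-sided exact paired | <0.1% | 0.2% | 3% |
| 4-0 | Fisher | <0.1% | 3% | 19% |
| 3-0 | tests in step 3 with p < 0.05 | 0.9% | 16% | 50% |

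**5. If subjects still in the trial are also counted.** The review covers cumulative data, so 7 or 8 treated subjects might contribute. At 30% the chances are then at most:
- 0.4% to 1.1% (two-sided exact paired, needs 6-0);
- 3% to 6% (one-sided exact paired or two-sided Fisher, 5-0);
- 35% to 45% where 3-0 still suffices, for example one-sided Mann-Whitney.

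These are upper bounds because the later subjects have not had all their injections.

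**6. Timing.** Five completers × 3 = 15 of 30 STS injections at least, whatever the accrual. With even accrual (an assumption):
- Ten months: one subject per month, fifth completer at 4 + 3 = 7.0 months. By then 7 subjects have been treated, with 15 + 2 + 1 = 18 injections.
- Eight months: one subject per 0.8 month, fifth completer at 3.2 + 3 = 6.2 months. By then 8 subjects have been treated, with 15 + 3 + 2 + 1 = 21 injections.

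**The case against.** Unit and direction are less open than the test. The rule compares lesions, each subject has one of each kind, and the word for a greater number points one way. That stands: the subject pair is the natural unit. Still, event counts are not excluded, a direction in words does not make p one-sided, and the wording could even be read as comparing the grade of events.

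A reader might go further, count 15 injections per arm, and infer that the same true rate could give anything from 0% to 83%. The documents do not support that range. The 83% needs injections treated as independent, a one-sided Mann-Whitney test, and a severe reaction at all three visits in every affected subject. Sections 8.2 and 13.1 withdraw subjects for serious STS events or intolerance, which makes three severe reactions each an unlikely pattern. If each affected subject contributes one event, the chance of three or more is again 16%.

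A reader might also infer that the trial cannot be stopped for harm, or that subjects are unprotected. Neither follows. Nothing bars suspension on clinical judgement after the review, and the subject-level safeguards are real.

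The 30% and 50% rates have no support in the documents. Section 14.1 foresees no major risk, and Section 9.2 caps the dose at 16 mg per visit. That is fair, and it limits what can be said about size. But the missing test, the 0.0625 floor and the 15-injection minimum need no assumed rate.

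The strongest point concerns blinding. One coin flip sets A and B for everyone, so decoding one subject decodes all. Any rule that compares STS with saline, including the present one, carries this risk, and an earlier look brings it forward. The remedy must say who counts.

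**Conclusion.** The concern holds and should be fixed. The rule's test and sidedness are unstated, and on 5 pairs the exact paired test triggers 0% (two-sided) or 0.2% (one-sided) of the time at a 30% rate. Across lesion-level tests the range at that rate is 0% to 16%. These figures assume a yes/no severe event per lesion, none on saline, and data from five subjects only; step 5 of the working shows the effect of counting more. The 18 to 21 injections before the look rest on even accrual. The conclusion concerns the prespecified rule, not the overall safety of the trial.

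**What to change.** **Section 12.1.** Replace p < 0.05 with a prespecified number of treated subjects, withdrawn subjects included, who have a severe or serious event on the STS lesion or systemically. Pause for review when it is reached. Show saline-lesion events alongside but do not count them. Agree the number with the IRB.

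As an illustration, take 2 of the first 5 treated. P(at least 2 of 5) is 47% at a 30% rate by the time those five finish. It is 2% at a 5% rate and 8% at 10%, which is the price in pauses for a chance cluster.

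**Timing.** Set the look by subjects treated, for example when the fifth treated subject reaches Week 4, before the second injection. With even accrual this falls at 5.0 or 4.2 months, two months sooner, after 12 or 13 STS injections: 6 or 8 fewer. The five subjects will have had 3, 3, 3, 2 and 1 injections. Assuming equal risk per injection, 1 − 0.7^(1/3) = 0.112, the chance of at least 2 affected by then is 36% rather than 47%.

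**Blinding.** Assign the count to the statistician or to the person who prepares the syringes, who already needs the code. The blinded investigator and the photograph reviewer should not learn it unless a pause is called. Some blinding risk remains, as it does with the current look.

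**Section 13.3.** Continue adverse-event follow-up after injections stop, unless consent is withdrawn.

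If the p-value is kept, state the test, sidedness and unit.

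The cost is a short amendment to two sections and brief follow-up of withdrawn subjects.
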